2.2.2. Pediatric Linaclotide Program

A total of 214 pediatric participants were treated with linaclotide in two Phase 2 dose-ranging studies in the FC and IBS-C pediatric populations (LIN-MD-62 and LIN-MD-63, respectively).

LIN-MD-62 was a Phase 2, double-blind, placebo-controlled, parallel-group, safety and efficacy study of a range of linaclotide doses administered to participants 6 to 17 years of age who fulfilled modified Rome III criteria for FC (refer to [Table 2-1](#) for dosing information). The objective of Study LIN-MD-62 was to evaluate the dose response, safety, and efficacy of 4 weeks of study intervention with 1 of 3 linaclotide doses (Dose A, B, and C) or 145 µg (as an exploratory objective in the adolescent participants 12 to 17 years of age using the approved adult dose) compared with placebo in pediatric participants, who fulfilled modified Rome III criteria for child/adolescent FC with the goal of selecting an optimal dose of linaclotide to evaluate in a confirmatory study.

Table 2-1 Dose Levels (in Micrograms) by Weight in Pediatric Participants Treated with Linaclotide in LIN-MD-62

Age Group (Dose, μ g)	Linaclotide Dose A N=36	Linaclotide Dose B N=41	Linaclotide Dose C N=39	Approved Adult Dose (exploratory) N=16
Participants 6 to 11 years				
18 to < 35 kg	9	18	36	-
\geq 35 kg	18	36	72	-
Participants 12 to 17 years				
	18	36	72	145

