7.1. Discontinuation of Study Intervention

A premature discontinuation will occur when a participant who gave voluntary assent and whose parent/guardian/LAR and/or caregiver gave consent ceases participation in the study, regardless of circumstances, before the completion of the protocol-defined study procedures.

Definitions of the standard terms that may lead to discontinuations are provided in [Appendix 5](#).

See the SoAs for data to be collected at the time of intervention discontinuation and follow-up and for any further evaluations that need to be completed.

Reasons for discontinuation from the study intervention and/or the study may include the following commonly used or other acceptable terms:

Commonly Used Terms	Other Acceptable Terms
AE	Death
Completed	Disease relapse
Lack of efficacy	Progressive disease
Lost to follow-up	Recovery
Other	Technical problems
Physician decision	Withdrawal by parent/guardian
Pregnancy	
Screen failure	
Site terminated by sponsor	
Study terminated by sponsor	
Withdrawal by participant	

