7.1.1. Removal of Individual Participants from Therapy or Assessment

Participants **must** be prematurely discontinued from the study for reasons of safety including those who experience:

- An SAE considered by the investigator or the sponsor to be possibly related or related to study intervention
- An AESI (evidence of significant volume depletion and/or significant electrolyte and/or ECG abnormalities that are considered by the investigator or sponsor to be related to diarrhea) related to the study intervention (ie, treatment-related AESIs)
- Pregnancy
- Presence of intentional overdose or intentional misuse per investigator discretion
- The occurrence of any other AE that in the opinion of the investigator or the sponsor is possibly related or related to the study intervention that represents a clinically significant safety risk to the participant

Participants **may** also be prematurely discontinued from the study for reasons of safety including those who experience:

- A vital sign, ECG, and/or laboratory abnormality judged to be clinically significant by the investigator and that, in the opinion of the investigator or the sponsor, is possibly related or related to the study intervention

- An intolerable AE (defined as an AE that subjectively would cause a patient to consider study withdrawal), see Section 8.3

Additionally, discontinuation of study intervention for abnormal liver function should be considered by the investigator when a participant meets the criteria for Hy's law or the appearance of abnormal laboratory test results suggesting severe drug-induced liver injury (DILI) (refer to [Appendix 9](#)), or if the investigator believes that it is in best interest of the participant.

All enrolled participants who prematurely discontinue from the study, regardless of cause, are required to return for the EOT study assessments. The EOT assessments are defined as completion of the evaluations scheduled for all participants.

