7.3. Lost to Follow Up

A participant will be considered lost to follow-up if he or she repeatedly fails to return for scheduled visits and is unable to be contacted by the study site.

The following actions must be taken if a participant fails to return to the clinic for a required study visit:

- The site must attempt to contact the participant and/or the parent/guardian/LAR and/or caregiver and reschedule the missed visit as soon as possible and counsel the participant on the importance of maintaining the assigned visit schedule and ascertain whether or not the participant wishes to and/or should continue in the study.
- Before a participant is deemed lost to follow-up, the investigator or designee must make every effort to regain contact with the participant (where possible, 3 telephone calls and, if necessary, a certified letter to the participant's last known mailing address or local equivalent methods). These contact attempts will be documented in the participant's source record.
- Should the participant continue to be unreachable, he/she will be considered to have withdrawn from the study.

8. Study Assessments and Procedures

- Study procedures and their timing are summarized in the SoA. Protocol waivers or exemptions are not allowed.
- Immediate safety concerns should be discussed with the sponsor immediately upon occurrence or awareness to determine if the participant should continue or discontinue study intervention.
- Adherence to the study design requirements, including those specified in the SoA, is essential and required for study conduct.

- All screening evaluations must be completed and reviewed to confirm that potential participants meet all eligibility criteria. The investigator will maintain a screening log to record details of all participants screened and to confirm eligibility or record reasons for screening failure, as applicable.
- Procedures conducted as part of the participant's routine clinical management (eg, blood count) and obtained before signing of the informed consent form (ICF) may be utilized for screening or baseline purposes provided the procedures met the protocol-specified criteria and were performed within the timeframe defined in the SoA.

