8.2.2. Vital Signs

Refer to the appropriate SoAs for the timing and frequency of height and vital signs measurements (Section 1.4 FC participants and Section 1.5 IBS-C participants).

Vital signs will be assessed as follows:

- Vital signs include weight, temperature (oral, rectal, or tympanic), and respiratory rate. Temperature may be recorded as oral, rectal or tympanic (ear). If possible, temperature should be obtained using the same method throughout the course of the study.
- Postural vital signs (supine and standing) include pulse rate and systolic and diastolic blood pressure. At all visits, postural vital signs must be obtained after participants have been in a supine position for at least 2 to 3 minutes, followed by a standing position for at least 1 minute.

8.2.3. **Electrocardiograms**

A standard 12-lead ECG will be performed at Screening (Visit 1) for participants who complete LIN-MD-62 and participants who enroll in LIN-MD-66 after > 28 days from last study intervention in LIN-MD-63 or LIN-MD-64. In addition, ECGs will be performed at the EOT Visit for all FC participants (Week 24) and all IBS-C participants (Week 52). ECGs will be performed and electronically transmitted to a central ECG laboratory for analysis according to the instructions provided by the central ECG laboratory. Measurements (in msec) will be recorded for the following parameters: heart rate, RR interval, PR interval, QRS duration, and uncorrected QT interval. QTcB (Bazett-corrected QT interval) and QTcF (Fridericia-corrected QT interval) will be calculated.

Participants with clinically significant ECG abnormalities considered to be secondary to diarrhea (ie, an AESI) must be reported to the sponsor within 24 hours on an SAE form if considered to be serious. Non-serious events do not require submission on an SAE form; rather, these events only need to be entered into the eCRF ([Appendix 3](#)).

If the AE is assessed as causally related to the use of study intervention, the participant should be discontinued from the study; however, the sponsor and investigator may discuss individual participants and AEs to make this determination ([Appendix 3](#)).

The overall interpretation and determination of the clinical relevance of ECG findings using the central ECG interpretation report will be the responsibility of the investigator and will be recorded in the participant's eCRF.

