10.2. Appendix 2: Clinical Laboratory Tests

Blood and urine samples for clinical laboratory tests will be collected as detailed in the SoAs (Section 1.4 and Section 1.5). During the screening period, the investigator will assess the clinical significance of any values that are outside the reference ranges provided by the central laboratory. Participants with abnormalities judged to be clinically significant will be excluded from the study.

Participants with clinically significant electrolyte abnormalities that are considered to be secondary to diarrhea (ie, an AE of special interest) must be reported to the sponsor within 24 hours on an SAE form if considered to be serious. Nonserious events do not require submission on an SAE form; rather, these events only need to be entered into the eCRF (Appendix 3). If the AE is assessed as causally related to the use of study intervention, the participant should be discontinued from the study; however, the sponsor and investigator may discuss individual participants and AEs to make this decision.

Clinical laboratory levels that will be measured are summarized in [Table 10-1](#).

The clinical significance of a positive urine drug screen will be assessed by the investigator. Participants will be excluded from study participation if urine drug screening results are positive for cocaine, barbiturates, opiates, or cannabinoids.

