10.3.1. Definition of AE

AE Definition

• An AE is any untoward medical occurrence in a patient or clinical study participant, temporally associated with the use of study intervention, whether or not considered related to the study intervention.• An AE can therefore be any unfavorable and unintended sign (including an abnormal laboratory finding), symptom, or disease (new or exacerbated) temporally associated with the use of study intervention. 
For the purpose of the site's data collection responsibilities, any untoward event that was reported from the time written consent was obtained until 30 days after the final protocol-defined study visit (or the last known dose of study intervention if the final visit does not occur) is to be considered an AE. Particular attention must be given to the AE of diarrhea, which was the most frequently reported AE in the adult linaclotide program. Details about AE reporting are provided below.
 
Examples of AEs are as follows:
 
• Changes in the general condition of the participant• Subjective symptoms offered by or elicited from the participant• Objective signs observed by the investigator or other study site personnel• All diseases that occur after signing the informed consent, including any change in severity or frequency of pre-existing disease• All clinically relevant abnormalities in laboratory values or clinically relevant physical findings that occur during the study schedule 
Please note medical procedures scheduled prior to consenting, but occurring during the study should not be captured as AEs, but should be listed in the medical history if related to a pre-existing condition.
 
AE of Special Interest (AESI)
 
An AESI (serious or nonserious) is one of scientific and medical concern specific to the sponsor's study intervention or program, which warrants ongoing monitoring and rapid

communication by the investigator to the sponsor. Such an event might warrant further investigation in order to characterize and understand it.

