The following AESIs have been identified for the study intervention in this protocol: significant volume depletion and/or significant electrolyte abnormalities and/or ECG abnormalities that are considered by the investigator or sponsor to be related to diarrhea. The investigator should contact the sponsor if there is any question whether the criterion for an AESIs has been met. All serious AESIs must be reported to the sponsor on an SAE form within 24 hours as noted below for SAEs.

Non-serious AESI do not require submission on an SAE form; rather, these events only need to be entered into the eCRF.

If the AESI is assessed as causally related to the use of study intervention, the participant should be discontinued from the study (Section 10.5 [Appendix 5](#)).

Potential Hy's Law Cases

For potential Hy's Law cases, refer to [Appendix 9](#).

Events Meeting the AE Definition

- Any abnormal laboratory test results (hematology, clinical chemistry, or urinalysis) or other safety assessments (eg, ECGs, radiological scans, vital signs measurements), including those that worsen from baseline, considered clinically significant in the medical and scientific judgment of the investigator (ie, not related to progression of underlying disease); for example:
 - The test result is associated with accompanying symptoms, and/or
 - The test result requires additional diagnostic testing or medical/surgical intervention, and/or
 - The test result leads to a change in study dosing (outside of any protocol-specified dose adjustments) or discontinuation from the study, significant additional concomitant drug treatment, or other therapy, and/or
 - The test result is considered to be an AE by the investigator or sponsor.
- Exacerbation of a chronic or intermittent pre-existing condition including either an increase in frequency and/or intensity of the condition
- New condition detected or diagnosed after study intervention administration even though it may have been present before the start of the study
- Signs, symptoms, or the clinical sequelae of a suspected drug-drug interaction
- Signs, symptoms, or the clinical sequelae of a suspected overdose of either study intervention or a concomitant medication. Overdose per se will not be reported as an AE or SAE unless it is an intentional overdose taken with possible suicidal/self-harming intent. Such overdoses should be reported regardless of sequelae.

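### Protocol 7.1.1 makes removal mandatory for a treatment-related, diarrhea-related AESI, while 8.2.3, 8.2.4 and Appendices 2 and 3 only advise it, three of them with a discussion clause

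*Protocol*

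**What the plan says.** Protocol 8.3.1 defines AESIs as significant volume depletion, significant electrolyte abnormalities or ECG abnormalities that the investigator or sponsor attributes to diarrhea. Five places then say what happens when such an event is attributed to the drug.

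- **7.1.1** puts it on the list of events for which removal from the study is a bolded *must*. The condition is that the AESI is "related to the study intervention (ie, treatment-related AESIs"). No exception is given.
- **8.2.3** (ECG) and **8.2.4** (electrolytes) say the participant *should* be discontinued if the event is causally related, then add: "however, the sponsor and investigator may discuss individual participants and AEs to make this determination".
- **Appendix 2** (Section 10.2, electrolytes) also says *should*, and ends: "however, the sponsor and investigator may discuss individual participants and AEs to make this decision".
- **Appendix 3** (Section 10.3.1, all AESIs) says: "If the AESI is assessed as causally related to the use of study intervention, the participant should be discontinued from the study". It has no discussion clause and refers the reader to Appendix 5.

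Section 7.1 describes Appendix 5 in these words: "Definitions of the standard terms that may lead to discontinuations are provided in". That appendix is a glossary of discontinuation reasons and holds no stopping rule.

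**The concern.** The rule decides whether a child stays on linaclotide after the one kind of harm the protocol has singled out for this drug. Section 7.1.1 grades its language deliberately: a *must* list, a *may* list, and a softer instruction to consider stopping for liver abnormalities. Against that background a site can reasonably read *should*, followed by a clause opening with *however*, as weaker than *must*.

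Two sites with the same case could therefore act differently, each able to cite the protocol. The site that kept dosing after discussion would have followed 8.2.3, 8.2.4 or Appendix 2 and breached 7.1.1. The difference would also reach the report to a small degree: SAP 9.2.2 and 9.2.5 summarize or list adverse events leading to discontinuation, and whether a case appears there would depend on which section the site had read.

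**Working it through.** No arithmetic applies. The point rests on comparing current text.

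| Place | AESIs covered | Strength | Discussion clause | What the discussion settles |
|---|---|---|---|---|
| 7.1.1 | All three types, related | must | No | – |
| 8.2.3 | ECG, related | should | Yes | *determination* |
| 8.2.4 | Electrolyte, related | should | Yes | *determination* |
| Appendix 2 | Electrolyte, related | should | Yes | *decision* |
| Appendix 3 | All three types, related | should | No | – |

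1. **Same events.** 8.2.3, 8.2.4 and Appendix 2 each label the event as an AESI, and each applies once it is judged causally related. That is the trigger in 7.1.1.

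2. **What the clause covers.** In 8.2.3 and 8.2.4 the clause comes in a sentence that opens with a causality condition, so the determination may fairly be read as the causality call. In Appendix 2 the word is *decision*, and it follows directly on the statement that the participant should be discontinued. The natural reading there is the decision to discontinue. On either reading, *must* against *should* remains.

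3. **Whether anything ranks the sections.** No sentence in the protocol says which wording prevails. The SAP contains no discontinuation rule for AESIs; 9.2.6 only tabulates and lists them. The opening of Section 8 rules out waivers and exemptions, which favors 7.1.1. The same list says "Immediate safety concerns should be discussed with the sponsor immediately upon occurrence or awareness", with the aim of deciding whether the participant continues or stops, which leaves room for the other view.

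4. **What is left after the other 7.1.1 criteria.** Related or possibly related SAEs are mandatory removals. So is any other related or possibly related event that is a clinically significant safety risk. Volume-depletion AESIs have no discussion clause, only the *should* in Appendix 3. What remains is mainly a non-serious, related ECG or electrolyte AESI not otherwise judged a clinically significant safety risk.

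5. **Interaction with liver events.** Appendix 9 also calls potential Hy's law cases AESIs, yet 7.1.1 and Appendix 9 ask only that discontinuation be considered for them. An unqualified *must* for every AESI in Appendix 3 would therefore create a new conflict.

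**The case against.** A reader might infer that the rules cannot both be followed. The documents do not support that. A site that removes every child with a treatment-related AESI satisfies all five places, because meeting *must* also meets *should*. A breach arises only if the discussion clause is used to continue dosing.

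The best defense is that the text can be harmonized. In 7.1.1 the AESI item on the *must* list requires the event to be related, while the *may* list takes in clinically significant ECG and laboratory abnormalities that are possibly related or related. A discussion of causality would then decide which list applies. Section 7.1.1 is also the section devoted to removal, and the ban on waivers supports treating it as controlling. This is a fair reading of 8.2.3 and 8.2.4. It fits Appendix 2 poorly, and it leaves *should* standing in four places.

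A reader might also infer that a child could be kept on drug without the sponsor knowing. That goes too far. Appendix 3 says AESIs, serious or not, warrant rapid "communication by the investigator to the sponsor", although non-serious ones need only an eCRF entry rather than an SAE form. The sponsor would usually know. What is open is whether the resulting discussion may end in continued dosing.

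Finally, one could align the text the other way and soften 7.1.1. That would be consistent too, but it would weaken an explicit safeguard for children and sit badly with the ban on waivers.

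**Conclusion.** The inconsistency is real and stands in current text. It is an inconsistency between sections, not a questionable design choice. It should be corrected, but its reach is narrow: mainly non-serious, treatment-related ECG or electrolyte AESIs that no other 7.1.1 criterion captures. The documents give no AESI rate for 24 or 52 weeks of treatment, so no number of affected children can be stated, and the finding does not depend on one. It affects no hypothesis, sample size, analysis population or error rate.

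The conclusion assumes that *must* and *should* differ in force, which the graded wording of 7.1.1 supports, and that *decision* in Appendix 2 refers to discontinuation. If that second assumption fails, the difference in force remains but the explicit route to continued dosing largely disappears.

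**What to change.** Make 7.1.1 the governing rule:

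- In 8.2.3, 8.2.4, Appendix 2 and Appendix 3, change *should* to *must*, limited expressly to the diarrhea-related AESIs defined in 8.3.1. Potential Hy's law cases then stay under Appendix 9 and the other 7.1.1 criteria, including the one for related SAEs, since 8.3.7 has these cases reported as SAEs.
- In 8.2.3, 8.2.4 and Appendix 2, confine the discussion clause to deciding whether the event is causally related or meets the AESI definition.
- In Appendix 3, refer to Section 7.1.1 for the rule.

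Section 6.6 and the *may* list in 7.1.1 need no change. The cost is wording only, in the next amendment or a clarification letter. The downside is a small loss of case-by-case discretion, which 7.1.1 as written already denies.

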8.3.1. Adverse Events of Special Interest

AESIs are defined as significant volume depletion and/or significant electrolyte abnormalities and/or ECG abnormalities that are considered by the investigator or sponsor to be related to diarrhea. The investigator should contact the sponsor if there is any question whether the criterion for an AE of special interest has been met. All AESIs must be reported to the sponsor as described in [Appendix 3](#).

8.3.2. Time Period and Frequency for Collecting Adverse Events, Serious Adverse Events, and Adverse Events of Special Interest Information

At each visit, participants are to be queried regarding any AEs or SAEs that have occurred since the previous visit. Participants will be asked to volunteer information with a nonleading question such as, "How do you feel since your last visit?" Study site personnel will record all pertinent information in the participant's eCRF.

- All SAE from the signing of the ICF until 30 days after the last dose of study intervention will be collected at the timepoints specified in the SoAs (Section [1.4](#) and Section [1.5](#)), and as observed or reported spontaneously by study participants.
- All AEs from the signing of the ICF until 30 days after the last dose of study intervention will be collected at the timepoints specified in the SoAs (Section [1.4](#) and Section [1.5](#)), and as observed or reported spontaneously by study participants.

- Medical occurrences that begin before the start of study intervention, but after obtaining informed consent will be recorded in the AE section of the eCRF.

All SAEs (including serious AESIs) will be recorded and reported to the sponsor or designee within 24 hours on an SAE form, as indicated in [Appendix 3](#). Nonserious AESIs do not require submission on an SAE form; rather, these events only need to be entered into the eCRF. The investigator will submit any updated SAE data to the sponsor within 24 hours of it being available.

Investigators are not obligated to actively seek AE or SAE information after conclusion of the study participation. However, if the investigator learns of any SAE including a death, at any time after a participant has been discharged from the study, and he/she considers the event to be reasonably related to the study intervention or study participation, the investigator must promptly notify the sponsor.

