8.3.7. Potential Hy's Law Cases

Criteria for possible Hy's law cases are as follows:

- ALT or AST $\geq 3 \times$ ULN AND
- Total bilirubin $\geq 2 \times$ ULN AND
- ALP $< 2 \times$ ULN

Study site personnel must report every participant who meets the criteria for potential Hy's law as SAEs (see [Appendix 9](#) for a detailed description on handling potential Hy's law cases and liver toxicity). Typically, all analytes will be obtained from the same sample, but they may come from multiple samples taken within a 24-hour period. This requirement applies from the time the participant signs the ICF for the study until 30 days after the last known dose of study intervention.

Additional details regarding liver safety assessments and follow-up are provided in [Appendix 9](#).

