9.2. Sample Size Determination

At least 120 participants are planned to be enrolled in this long-term safety study, LIN-MD-66. However, the actual number of participants in this study will depend on the number of participants who complete the lead-in studies (LIN-MD-62, LIN-MD-63, and LIN-MD-64) and who are eligible to be enrolled into this long-term study after fulfilling the eligibility criteria. The sample size in this study is not driven by any statistical consideration.

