If any of the following criteria are met, discontinuation of study intervention should be considered (if indicated, prior to receipt of confirming retest biochemistry laboratory test results) and the sponsor notified of the discontinuation:

- ALT or AST $\geq 3 \times$ ULN and the participant is symptomatic with the appearance of fatigue, nausea, vomiting, right upper quadrant pain or tenderness, fever, rash, or eosinophilia ($> 5\%$)
- ALT or AST $\geq 3 \times$ ULN and total bilirubin $> 2 \times$ ULN or INR > 1.5
- ALT or AST $\geq 5 \times$ ULN for more than 2 weeks
- ALT or AST $\geq 8 \times$ ULN

If the study intervention is discontinued, the participant may be re-challenged with study intervention only after consultation with the Allergan MSP. All participants showing potential DILI should be followed until all abnormalities return to normal or to the baseline state.

Reporting of Potential Hy's Law Cases

Potential Hy's law cases are defined by biochemical test results of hepatocellular injury and impaired hepatic function. They are considered Adverse Events of Special Interest (AESIs) and should be evaluated and followed further (ie, close monitoring initiated) to determine whether these laboratory abnormalities are indicative of DILI. As indicated above, discontinuation of study intervention should also be considered. Criteria that identify a potential Hy's law case are as follows:

- ALT or AST $\geq 3 \times$ ULN AND
- Total bilirubin $\geq 2 \times$ ULN AND
- Alkaline phosphatase $< 2 \times$ ULN

Sites must report every participant who meets the Hy's law criteria if this occurs within the time the participant signs the ICF until 30 days after the last dose of study intervention.

A laboratory alert for a potential DILI case will be sent immediately to the sponsor and investigators when the above criteria have been met, even if no clinical symptoms have been experienced. In addition, both an SAE and Adverse Event of Interest Abnormal Liver Function Reporting Form (GPSE PVOPS-F-01-28) for all potential Hy's law DILI cases should be completed as soon as possible (within 24 hours of learning that a participant fulfills the potential

CONFIDENTIAL
Linaclotide

Protocol LIN-MD-66, Amendment 2

Hy's law criteria) and submitted to the sponsor as noted in [Appendix 3](#). The eCRF pages associated with the potential Hy's law cases must be completed within 7 calendar days.

Approval Date: 30-Apr-2021 22:48:03 (GMT)

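### Potential Hy's law cases fall under both a mandatory and a discretionary discontinuation rule, with no precedence stated if possibly related, and only Appendix 9 calls them AESIs

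*Protocol*

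**What the plan says.** Protocol 8.3.7 sets the status of these cases: "Study site personnel must report every participant who meets the criteria for potential Hy's law as SAEs". Appendix 9 agrees and asks for "both an SAE and Adverse Event of Interest Abnormal Liver Function Reporting Form" within 24 hours.

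Protocol 7.1.1 then contains two rules that can reach such a case. Its list of mandatory removals from the study includes "An SAE considered by the investigator or the sponsor to be possibly related or related to study intervention". A later paragraph of the same section says "discontinuation of study intervention for abnormal liver function should be considered by the investigator when a participant meets the criteria for Hy's law". Appendix 9 uses the same discretionary wording twice, once for its four liver criteria and again in its paragraph on potential Hy's law cases. It adds that, where study intervention has been stopped, "the participant may be re-challenged with study intervention only after consultation with the" sponsor's medical safety physician.

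On classification, Appendix 9 says of potential Hy's law cases: "They are considered Adverse Events of Special Interest (AESIs) and should be evaluated and followed further". Protocol 8.3.1 reads differently: "AESIs are defined as significant volume depletion and/or significant electrolyte abnormalities and/or ECG abnormalities", with the link to diarrhea as a condition. The AESI item in 7.1.1 and the AESI text in Appendix 3 use the same diarrhea-related list, and SAP 9.2.6 names nothing else. SAP 9.3 has its own summary of potential Hy's law cases.

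**The concern.** A potential Hy's law case is a possible severe drug-induced liver injury, here in a child. Two sites that both follow the protocol could handle the same possibly related case differently. One removes the participant from the study under the mandatory list. The other weighs stopping treatment under the liver paragraph and may later discuss re-challenge. The two rules also differ in object: the mandatory one concerns leaving the study, the liver text concerns stopping study intervention.

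The classification mismatch has a reporting consequence. A programmer working from 8.3.1 leaves potential Hy's law cases out of the AESI table, and one working from Appendix 9 puts them in.

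**Working it through.** No arithmetic applies. The study has no powered comparison ("The sample size in this study is not driven by any statistical consideration"), and there is no stated figure to reproduce. The check is a side-by-side reading.

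**Step 1: is every potential Hy's law case an SAE?** Yes. Section 8.3.7 says so, and Appendix 9 requires an SAE form for each. The SAE item on the mandatory list in 7.1.1 is therefore always in play, subject only to causality.

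**Step 2: apply both rules by causality.**

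| Causality of the case | SAE item, mandatory list in 7.1.1 | Liver text in 7.1.1 and Appendix 9 | Compatible? |
|---|---|---|---|
| Judged unrelated | Not triggered | Stopping treatment is discretionary; re-challenge open after consultation | Yes |
| Not yet assessed | Not yet triggered | Same | Yes, for the time being |
| Judged possibly related or related | Removal from the study is mandatory | Same | No |

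The middle row should be brief. Appendix 3 asks for a causality assessment before the first SAE transmission, and SAEs are due within 24 hours.

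**Step 3: does any text settle the last row?** None was found. The liver paragraph in 7.1.1 is introduced as an addition to the lists, not as an exception, and it carries no causality condition. Appendix 9 does not refer to the mandatory list. Its own standing is also unclear: footnote a of Table 10-1 describes it as holding stopping criteria and required actions, while its title calls the actions suggested.

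**Step 4: is a potential Hy's law case an AESI?**

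| Place | Answer |
|---|---|
| Protocol 7.1.1, AESI item | No; diarrhea-related events only |
| Protocol 8.3.1 | No; same definition |
| Appendix 3 (10.3.1) | Not in the list; Hy's law has its own heading, which points to Appendix 9 |
| Appendix 9 | Yes |
| SAP 9.2.6 | Not named |
| SAP 9.3 | Summarized separately, under laboratory data |

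This mismatch does not depend on causality. With no diarrhea-related AESI, one potential Hy's law case makes the AESI count 0 under 8.3.1 and 1 under Appendix 9. The label also brings in another standard for a related case: Appendix 3 says a participant with a related AESI should be discontinued from the study, where 7.1.1 uses mandatory wording.

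**Step 5: how often could this bite?** In all four schedules of activities, post-baseline chemistry is scheduled only at EOT (Week 24 for FC, Week 52 for IBS-C). For a completer, a scheduled finding comes when treatment is ending and stopping is largely moot. The conflict arises during treatment only through unscheduled or local tests, which 8.2.4 and Appendix 2 allow.

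**The case against.** The best defense is that the rules are layered. The mandatory item applies once an SAE is judged possibly related or related, and the liver paragraph adds a trigger for cases not yet assessed or judged unrelated. Appendix 9 fits this, since it contemplates stopping before the retest result is back and during a work-up for other causes. On this view discretionary wording never cancels mandatory wording, and all that is missing is a cross-reference. That stands for the first two rows of the Step 2 table. It fails for the third: the liver text has no causality condition and is aimed at suspected drug-induced injury, so its discretion and re-challenge provision reach the very cases that the mandatory rule removes. The alternative, that the specific liver rule overrides the general one, is stated nowhere.

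Several stronger readings are tempting but unsupported:

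- A reader might infer that 7.1.1 itself permits re-challenge. It does not mention it. The provision is in Appendix 9 only and follows a stop under any of the liver criteria, so it can operate without touching the mandatory list.
- A reader might infer that cases could vanish from the report. SAP 9.3 summarizes them from first dose to 30 days after last dose, and SAP 9.2.5 lists SAEs.
- A reader might make something of the bilirubin limits in Appendix 9 (above 2 × ULN in a stopping criterion, at or above 2 × ULN in the Hy's law definition). No instruction changes: the Hy's law paragraph carries the same advice to consider stopping.

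It is also fair to say that SAP 9.2.6 introduces its list with *including*, so it is not expressly closed. That leaves the programmer without an answer; it does not supply one.

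**Conclusion.** The protocol contradicts itself on two points. First, for a potential Hy's law case judged possibly related or related, mandatory removal from the study cannot be squared with discretionary stopping of treatment or with re-challenge, and nothing states which governs. Second, Appendix 9 and the AESI definitions elsewhere disagree on whether such a case is an AESI.

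The size is limited. The first conflict is conditional on causality, and few on-treatment cases are expected given the EOT-only chemistry. The documents give no expected rate of Hy's law cases, so that expectation rests on the testing schedule alone. The second affects the label and the AESI table, not whether a case is reported. It remains worth correcting because each case is a potential severe liver injury in a child and the instructions for a possibly related one are incompatible. No view is taken here on which clinical rule is right.

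**What to change.** Reconcile Protocol 7.1.1, 8.3.7 and Appendix 9 so that one discontinuation rule applies to a potential Hy's law case. The text should make explicit the causality condition, whether the rule concerns study intervention or the study, and how it relates to the re-challenge provision. The content of that rule is for the sponsor and investigators to decide. The description of Appendix 9 in footnote a of Table 10-1 should be brought into line at the same time.

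Reconcile the AESI definition across 7.1.1, 8.3.1, Appendix 3, Appendix 9 and SAP 9.2.6, stating plainly whether a potential Hy's law case is an AESI, and count it accordingly. The separate summary in SAP 9.3 can stay as it is.

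The cost is wording in the next protocol amendment and one line in the SAP. These edits need no new visits, samples or participants.
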